3.2 Participants

We will include a total of 40 middle aged adults (35-60 years) of all races and ethnicities in this study. Inclusion/exclusion criteria are listed below.

Inclusion criteria:

- Age ≥ 35 and ≤ 60 years;
- BMI ≥ 25 and ≤ 35 kg/m²;
- Weight stable in last 3 months (loss or gain $<4\%$);
- Hemoglobin A1C (HbA1C $\leq 6.4\%$);
- Fasting plasma glucose concentration <126 mg/dl;
- For the safety of the participant and proper consent of the procedures, subjects must be able to speak and understand English to participate in this study;
- Stable medication/supplement use for 3 months prior to study;

Exclusion criteria:

- Use of medications that are known to affect the study outcome measures (e.g., NSAIDs, corticosteroids) or increase the risk of study procedures (e.g., anticoagulants) that cannot be temporarily discontinued for this study;
- Strict dietary patterns (e.g., vegan, keto);
- Consuming >14 alcoholic drinks per week;
- Use of cigarettes (or other tobacco products) in last 3 months;
- Engaged in high level of competitive exercise (e.g., iron man, marathons, powerlifting);
- Diagnoses of active malignancy, congestive heart failure, diabetes mellitus or chronic obstructive pulmonary disease;
- Any inflammatory diseases (e.g., autoimmune diseases, coeliac disease, glomerulonephritis, hepatitis, inflammatory bowel disease, arthritis);
- Use of antibiotics in last 60 days;
- Pregnant or planning to become pregnant in the next 5 months;
- Lactating women;
- Persons who are unable or unwilling to follow the study protocol or who, for any reason, the research team considers not an appropriate candidate for this study, including non-compliance with screening appointments or study visits.

* Participants that are pregnant or planning on becoming pregnant in the next 5 months are excluded. The justification is the documented alterations in metabolism that occur during pregnancy ⁶, which would impact our metabolomics analysis in this study.

Exclusion criteria will primarily be identified by way of a phone/email screen and routine bloodwork (when determined eligible based on the phone-screen and/or email-screen and after being consented).

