Consent Visit (Week 1. Duration: 1 hour): This visit can be done virtually through Zoom or occur in person in the Center for Human Nutrition Studies (CHNS) at Utah State University. Potential subjects will attend a consent session conducted by a trained member of the research staff to present the details of the study. Interested participants will complete the informed consent process privately with study staff. We will allow up to 60 minutes for the subjects to read the consent and ask questions. If a subject wants additional time to think about the study, this will be allowed. The study team will contact the subject three days after the initial consent visit ask if he or she has come to a decision. No study procedures will take place before written consent is obtained. To minimize subject burden, participants will be instructed during the phone screen that they have the opportunity to combine the consent visit with their screening visit (see below). If participants wish to combine visits, they are instructed that they will have to perform this visit in the morning after an overnight, 12-hour fast.

Screening Visit (Week 1. Duration: 2 hours): Study participants will be asked to come in during the morning after an overnight, 12-hour fast. During this visit the following will take place:

- **Blood Draw:** A trained phlebotomist (the PI) will draw a fasted blood sample for routine blood work to ensure the participant qualifies for the study. Using a small needle, 15 ml blood will be collected from a vein in the participant's forearm or hand. Blood samples will be sent to LabCorp to be analyzed for HbA1C, Glucose, Basic Metabolic Panel (BMP), and Lipid panel. The blood of women of childbearing potential will be subject to a pregnancy test (hCG) as part of this screening blood draw. This will also occur through LabCorp.
- **Body mass and height.** Height (cm) will be measured without shoes. Body mass (kg) will be measured without shoes, coats, or sweaters. BMI will be calculated as body mass (kg) / height (m)².
- **Blood pressure:** A blood pressure measurement will be taken using an automated upper arm blood pressure monitor (Omron BP5250). A total of three measurements will be taken and the average value of those will be collected for participant characterization.
- **Questionnaires:** Participants will be asked to complete the following questionnaires:

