4. SUBJECT RECRUITMENT AND COMPENSATION

4.1 Recruitment

Subjects will be recruited by posting flyers in designated areas around USU's campus, and through advertisement on public Facebook pages (Cache Valley Classifieds and/or Marketplace), local NextDoor pages, Craigslist, Reddit (R/Logan), Instagram, and/or Twitter. In the advertisement, potential subjects for this study will be directed to contact the study team by email or phone to obtain more information about the study, if interested. Participants who are interested will be provided with a copy of the informed consent by email. When the participant expresses interest in being in the study, the study team member will confirm, by telephone, that the participant meets most of the inclusion/exclusion criteria (ones that can be determined without the need for a blood draw) before scheduling him/her for a consent meeting. Subjects will attend a one-on-one information/consent session that will be conducted by a trained member to present the details of the study. We anticipate that we will need to telephone screen approximately 150 people and that approximately 30 will be consented. We will enroll up to 40 participants to meet our goal of having at least 18 participants complete the study.

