- **Power Calculations:** Using untargeted metabolomics for our power calculations of the number of participants we need to recruit, we assume a P -value ≤ 0.05 , Q -value ≤ 0.3 , and standard deviation of 0.3 based on previous work^{7,8}. 600 metabolites are typically identified and a conservative estimation in longer-term dietary intervention trials is that 40-80 metabolites will be significantly different with a mean of 0.157 (18 % difference). An $n=34$ per group is expected to provide true discovery rates ranging from 89-93 % assuming differences in 40-80 metabolites. Assuming a drop-out of 25%, the final number of participants we anticipate to recruit is $N=40$.

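### Section 7 bases its true discovery rates on 34 completers, but its own N=40 and 25% drop-out give 30; Section 4.1's forecast of about 30 consented cannot supply 40

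*Combined protocol and SAP*

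**What the plan says.** All references are to the combined protocol and SAP.

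- **Section 7, Power Calculations.** The basis is metabolomics: "Using untargeted metabolomics for our power calculations of the number of participants we need to recruit". The inputs are P ≤ 0.05, Q ≤ 0.3, a standard deviation of 0.3, a mean difference of 0.157, and 40 to 80 changed metabolites out of 600. A sample of n=34 "per group is expected to provide true discovery rates ranging from 89-93" percent. The paragraph ends: "Assuming a drop-out of 25%, the final number of participants we anticipate to recruit is" N=40.
- **Section 7, Statistical analysis.** The two diets are compared within person by paired t-tests on change scores.
- **Section 3.2.** "We will include a total of 40 middle aged adults (35-60 years"). Eligibility is checked partly by "routine bloodwork (when determined eligible based on the phone-screen and/or email-screen and after being consented").
- **Section 3.4, Consent Visit.** "No study procedures will take place before written consent is obtained".
- **Section 4.1.** "We anticipate that we will need to telephone screen approximately 150 people and that approximately 30 will be consented". The next sentence reads: "We will enroll up to 40 participants to meet our goal of having at least 18 participants complete the study".

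**The concern.** There are two separate discrepancies.

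The first lies inside the power paragraph. The stated rates belong to 34 people contributing data on both diets, but the recruitment number and drop-out rate in the same paragraph do not produce 34.

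The second lies between sections. Someone who has not consented cannot be included, and some who consent will fail the bloodwork. The number consented must therefore be at least the number included, plus any screen failures. A forecast of about 30 does not fit a planned 40.

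The number of completers sets the precision of the paired comparison, and the power paragraph is the only place where the plan justifies its size. It covers only the metabolomics objective (objective 2 in Section 2). As it stands, a reader can take the planned number of completers to be 34 (stated), 30 (implied by Section 7), about 22 (implied by the consent forecast) or 18 (the minimum goal). The stated rates apply only to the largest of these.

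**Working it through.** **Inputs.** n=34, drop-out 25% and N=40 (Section 7); 40 included (Section 3.2); 150 phone-screened, about 30 consented and at least 18 completers (Section 4.1).

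**Step 1: what 34 counts.** Each completer eats both diets and the test is paired, so 34 per group means 34 completers. Two parallel groups would need 2 × 34 = 68, which is further from 40.

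**Step 2: try to reproduce N=40.**

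| Route | Calculation | Result |
|---|---|---|
| Divide by the retention rate | 34 / (1 − 0.25) = 45.3 | 46 |
| Common shortcut | 34 × 1.25 = 42.5 | 43 |
| Completers from N=40 at 25% | 40 × 0.75 | 30 |
| Drop-out that fits 34 of 40 | 1 − 34/40 | 15% |

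Neither inflation gives 40. N=40 is exactly what 30 completers would need (30 / 0.75 = 40).

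**Step 3: the consent forecast.** 30 consented is 10 short of 40 before any screen failure. If all 30 started, 30 × 0.75 = 22.5, or about 22 completers. The forecast yield is 30/150 = 20%, so 40 consented would need 40 / 0.20 = 200 phone screens.

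**Step 4: effect on precision.** For a given SD of the paired difference, its standard error is proportional to 1/√n. Relative to n=34:

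- n=30: √(34/30) = 1.065, about 6% larger
- n=22: √(34/22) = 1.243, 24% larger
- n=18: √(34/18) = 1.374, 37% larger

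**Step 5: effect on the stated rates (illustration only).** The sponsor's figure cannot be recomputed, because Section 7 does not name the method, define the rate or say what the SD of 0.3 refers to. Suppose that the rate is the average chance of detecting a truly changed metabolite. Take a two-sided paired t-test (noncentral t), and scale the standardised difference d so that n=34 gives exactly 89% or 93%. Pairing 89% with 40 changed metabolites and 93% with 80 is also an assumption.

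| Criterion | d | n=34 | n=30 | n=22 | n=18 |
|---|---|---|---|---|---|
| P ≤ 0.05 only | 0.563 | 89% | 84.6% | 71.2% | 61.5% |
| P ≤ 0.05 only | 0.607 | 93% | 89.5% | 77.5% | 68.0% |
| P ≤ 0.05 and Q ≤ 0.3, 40 changed | 0.620 | 89% | 83.4% | 63.1% | 45.9% |
| P ≤ 0.05 and Q ≤ 0.3, 80 changed | 0.607 | 93% | 89.2% | 74.2% | 60.5% |

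The Q ≤ 0.3 rows set the threshold as Benjamini-Hochberg does, counting all 600 metabolites as potential false positives. Counting only the unchanged ones (560 or 520) gives 83.5/63.5/46.8% for 40 changed and 89.5/77.5/65.4% for 80 changed. Across all rows the ranges are about 83–90% at n=30, 63–78% at n=22 and 46–68% at n=18.

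**The case against.** The strongest reply concerns importance. The slip in Section 7 costs 6% in standard error, and the cheapest repair changes neither the design nor the number of participants. The larger figures come from the recruitment forecast and the goal of 18. The forecast feeds no analysis, and 18 is a floor. This is fair about size, and the 34-to-30 gap alone is modest. It does not remove the fault: the only justification for the trial's size quotes rates at a number its own inputs do not deliver.

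A second objection is that the illustration rests on one reading of an undefined term. If the true discovery rate means the share of discoveries that are real, the fall is smaller. Taking d = 0.157/0.3 = 0.523 and P ≤ 0.05, that share goes from about 72% to 71% with 80 changed metabolites, or from 55% to 53% with 40, between n=34 and n=30. Plain paired power at that d is 84% at n=34 and 79% at n=30. None of these gives 89–93%. The objection stands, so the illustration should carry no weight beyond showing direction and rough scale. The standard-error ratios do not depend on it.

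Third, Section 4.1 gives an approximate forecast and words its 40 as a ceiling. The figure of 22 is thus an expectation, not a hard cap. That also stands. But Sections 3.2 and 7 give 40 as the planned number, and approximation does not cover a shortfall of 10 in 40.

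Finally, the documents do not show that 34 is the mistaken input, so restating the rate at n=30 is a choice. The fix therefore keeps the other routes open.

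**Conclusion.** The concern holds and must be fixed. Section 7's figures of 34, 25% and 40 are incompatible: its own inputs give 30 completers, 4 fewer than the number behind the stated rates. Section 4.1's roughly 30 consented cannot supply the 40 in Sections 3.2 and 7, and implies about 22 completers at the plan's drop-out rate.

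Confidence is high for this participant arithmetic, which needs only the crossover design, the paired test and the order of consent and screening, all stated in the documents. The cost in precision is modest at 30 completers and material at 22. How far the true discovery rate itself falls cannot be established from the documents. The goal of at least 18 is a minimum and not a further arithmetic error, but it is only 18/34 = 53% of the number on which the rates rest.

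**What to change.** **Section 7.** Keep N=40 and 25% drop-out, state 30 expected completers, rerun the sponsor's own calculation at n=30, and report that rate in place of the one at n=34. Name the method, define the true discovery rate, and say what the SD of 0.3 refers to.

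**Section 4.1.** Set the consent forecast above the number to be enrolled by a stated screen-failure allowance, with a phone-screen number to match: at least 200 at the plan's own 20% yield, more once screen failures are allowed for. Either align the completer goal with the expected completers, or label 18 as a minimum and give the rate expected there.

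**If another input was the mistake.** If it was the drop-out rate, correct and justify it; 15% gives 34 of 40. If 34 completers at 25% drop-out is a real requirement, change 40 to 46. Whichever route is taken, Sections 3.2, 4.1 and 7 must agree.

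**Cost.** The default route takes one rerun, some rewording and probably a slightly less favourable stated rate. It adds no participants, and the extra phone screens are what N=40 already implies. The 46 route adds 6 participants, each with 2 × 44 = 88 days of provided food and up to $1000 compensation (Section 4.2), and at least 46 / 0.20 = 230 phone screens.

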8. DATA STORAGE AND CONFIDENTIALITY

Clinical study data (including screening data, food logs, questionnaires, satiety responses, bloodwork) will be collected and managed using REDCap (Research Electronic Data Capture). REDCap is a secure web application designed to support data capture for research studies, providing user-friendly web-based case report forms, real-time data entry validation (e.g. for data types and range checks), audit trails and a de-identified data export mechanism to common statistical packages (SPSS, SAS, Stata, R/S-Plus). The system was developed by a multi-institutional consortium initiated at Vanderbilt University. REDCap servers are hosted in the College of Education & Human Services at Utah State University, where data will be stored and processed. REDCap data collection projects rely on a thorough study-specific data dictionary defined in an iterative self-documenting process by all members of the research team. This iterative development and testing process results in a well-planned data collection strategy for individual studies. REDCap is flexible enough to be used for a variety of types of research and provides an intuitive user interface for database design and data entry. The exception is Garmin Activity Data which will be stored on the Garmin Website and accessible to the study team by logging in to Garmin's website using a coded email in accordance with participant codes (no personal identifiers will be used). The data will be downloaded and stored (on USU's Box Drive) periodically by the research team. At the end of the study and after all data is downloaded, the account will be removed. Coded clinical data will be stored indefinitely on REDCap and/or USU's Box. The enrollment log, with participant names/addresses that can be linked back to participant codes, which is kept on the [name] Lab Shared Drive on USU's box will be destroyed 3 years after completing the study. It is anticipated that all manuscripts will be published at that time and have been sent to interested study participants. Online activity always carries with them a risk of breach. Participants will be made aware of these potential threats and risks to their confidentiality.

Biospecimens will be stored in a -80°C freezer at the Center for Human Nutrition Studies for the duration of sample collection. All samples will be stored using coded labels. This will be accomplished by removing or recoding, direct and indirect, identifiers in the bio specimen

data. Some examples of identifiers that will be removed to prevent the risk of association of a participant to their data are: names and initials, birthdate, telephone numbers, email addresses, and any other unique identifying number, code, or characteristic. Blood samples collected during screening will be sent to LabCorp for routine bloodwork. Once all biospecimens have been collected from all participants, all biospecimens will be transported to a -80°C freezer in the Nutrition and Food Science building for long-term storage (maximum of 20 years). Any participant coded analytical data (including inflammatory biomarkers, metabolomics data, and analyzed food log data) will be kept on the [name] Lab Drive at USU's Box Drive to be accessed only by [name] [name] and his study staff. Study records that identify subjects will be kept confidential as required by law. Federal Privacy Regulations provide safeguards for privacy, security, and authorized access. Except when required by law, they will not be identified by name, social security number, address, telephone number, or any other direct personal identifier in study records disclosed outside of Utah State University. For records disclosed outside of USU, they will be assigned a de-identified code number. The key to the code will be kept on the [name] Lab Drive at USU's Box Drive.

Any electronically collected data using third-party software (Garmin) will be collected using the company's platform and the data will subsequently be downloaded by the study team and stored on the [name] Lab Drive at USU's Box Drive. Information collected by Garmin is subject to their terms of use and any information sent to a third-party software carries potential security risks. Some apps/third party software may be able to perform hidden functions or may have security flaws that allow unauthorized access to information. We are unable to fully assure participants that the information contained within or sent to this mobile app/third-party software are inaccessible or tamper-resistant. Nor can we guarantee that information will not be illicitly stored outside of Utah State University. Apps/third party software may include the capability of sending/receiving information with other apps/third party software, including social networking apps, or websites. If participants give permission to share their data, either inadvertently or deliberately, the terms of use for those apps/websites apply. Participants will be advised to limit personal identifiers entered into mobile applications/third party software only to those that they wish to voluntarily share with others. To protect the PHI of the participants, each participant will be assigned a unique subject ID. To collect physical activity data through Garmin, we will create a generic email account, based on the subject's ID code, which will be used to login to the activity monitor mobile app.

9. DATA SAFETY AND MONITORING

All study members will have completed CITI- and other institutional training pertinent to the study. Any unanticipated problems will be reported to the USU IRB by the PI as per institutional policy.

